8.4 Exclusion Criteria

Part 1:

Subjects to whom any of the following applies will be excluded from the study:

1. Any clinically significant abnormality or vital sign abnormality at physical examination (including baseline high blood pressure [140/90] after 3 repeated measurements or high random blood sugar [non-fasting]), clinically significant abnormal laboratory test results or positive test for HIV, hepatitis B, or hepatitis C found during medical screening.

2. Any acute or chronic ongoing illness which, in the judgement of the investigator, may preclude the subject's participation.
3. Any subject that has an active COVID-19 infection (positive COVID-19 test: nasal/oropharyngeal swab and/or positive serum antibody response) at screening, or Day 1, or has been in close contact with someone who has an active COVID-19 infection, or has recovered from a previous COVID-19, SARS-CoV--1, or MERS infection.
4. Positive pregnancy, urine drug screen, or alcohol breath test at screening.
5. Known history of allergic reactions or hypersensitivity to vaccines, or to any excipient in the formulation (including the adjuvant, MF59C.1).
6. Presence of a known, or suspected, impairment of the immune system including, but not limited to, HIV, autoimmune disorders, immunosuppressant therapy, and diabetes mellitus.
7. History of a known, or suspected, respiratory system disorder including, but not limited to, cystic fibrosis, reactive airway disease, emphysema, chronic bronchitis, chronic obstructive pulmonary disease (COPD), or asthma, excluding childhood asthma.
8. History of significant alcohol abuse within 12 months year prior to screening.
9. Positive test for drugs of abuse (such as marijuana/tetrahydrocannabinol [THC] products, amphetamine, methamphetamine, methadone, barbiturates, benzodiazepines, cocaine, opiates, methylenedioxymethamphetamine [MDMA], or phencyclidine [PCP]) at screening, prior to dosing, or a history of drug abuse within 12 months prior to screening.
10. Participation in a clinical research study involving the administration of an investigational, or marketed, drug or device within 30 days prior to receiving the first treatment administration, or administration of a biological product in the context of a clinical research study within 90 days prior to the first dosing, or concomitant participation in an investigational study involving no drug, vaccine, or device administration, or intent to participate in another clinical study at any time during the conduct of the study.
11. Use of medications for the timeframes specified below, with the exception of hormonal contraceptives and medications exempted by the Investigator on a case-by-case basis because they are judged to interfere with subject safety e.g., topical drug products without significant systemic absorption are permissible:
 - a. Prescription medication within 14 days prior to the first dosing;
 - b. Any medication, or treatments, that may affect the immune system such as allergy injections, immunoglobulin, interferon, immunomodulators, cytotoxic drugs, or other drugs known to be frequently associated with significant major organ toxicity within 90 days prior to enrolment;
 - c. Any registered vaccine administered within 30 days prior to enrolment in the study, or who plan to receive any non-study vaccines within 28 days of the second dose of the study vaccine

- d. Any other investigational coronavirus vaccine i.e. SARS--CoV-1, SARS--CoV-2, MERS etc. at any time prior to, or during, the study.
 - e. Over-the-counter products within 7 days prior to the first dosing, with the exception of the occasional use of paracetamol (up to 2 g daily) and standard dose vitamins.
12. Donation of plasma within 7 days prior to dosing. Donation or loss of blood (excluding volume drawn at screening) of 50 mL to 499 mL of blood within 30 days, or more than 499 mL within 56 days prior to the first dosing.
 13. Receipt of blood products within 2 months prior to the first study treatment administration (Day 1), or planned receipt of blood products during the study period.
 14. Breast-feeding subject, or subject who plans to breastfeed from the time of first dose through 60 days after last study treatment administration.
 15. Presence of tattoos, scarring, skin discoloration, or any other skin disturbances at the injection site which, in the opinion of the Investigator, may inhibit the ability to effectively perform an injection site assessment.
 16. Employee or immediate relative of an employee of the clinical site, any of its affiliates or partners, or Syneos Health.
 17. Any reason which, in the opinion of the Investigator, would interfere with the primary study objectives or prevent the subject from participating in the study.

Part 2

Subjects to whom any of the following applies will be excluded from the study:

1. Any clinically significant abnormality or vital sign abnormality at physical examination, or uncontrolled hypertension in adults aged ≥ 56 years and older, or high random blood sugar [non-fasting]), clinically significant abnormal laboratory test results or positive test for HIV, hepatitis B, or hepatitis C found during medical screening.
2. Any acute or chronic ongoing illness which, in the judgement of the investigator, may preclude the subject's participation.
3. Any subject that has an active COVID-19 infection (positive COVID-19 test: nasal/oropharyngeal swab and/or positive serum antibody response) at screening, or Day 1, or has been in close contact with someone who has an active COVID-19 infection, or has recovered from a previous COVID-19, SARS-CoV-1, or MERS infection.
4. Positive pregnancy, urine drug screen, or alcohol breath test at screening.
5. Known history of allergic reactions or hypersensitivity to vaccines, or to any excipient in the formulation (including the adjuvant, MF59C.1).

6. Presence of a known, or suspected, impairment of the immune system including, but not limited to, HIV, autoimmune disorders, immunosuppressant therapy, and diabetes mellitus.
7. History of a known, or suspected, or currently unstable medical condition that may expose the participant to an increased risk for severe SARS-CoV-2 disease, such as a respiratory system disorder including, but not limited to, cystic fibrosis, reactive airway disease, emphysema, chronic bronchitis, chronic obstructive pulmonary disease (COPD), or asthma, excluding childhood asthma, uncontrolled hypertension, ischemic or structural heart disease, chronic kidney disease, chronic liver disease, endocrine disorder and neurological illness.
8. History of significant alcohol abuse within 12 months prior to screening.
9. Positive test for drugs of abuse (such as marijuana/tetrahydrocannabinol [THC] products, amphetamine, methamphetamine, methadone, barbiturates, benzodiazepines, cocaine, opiates, methylenedioxymethamphetamine [MDMA], or phencyclidine [PCP]) at screening, prior to dosing, or a history of drug abuse within 12 months prior to screening.
10. Participation in a clinical research study involving the administration of an investigational, or marketed, drug or device within 30 days prior to receiving the first treatment administration, or administration of a biological product in the context of a clinical research study within 90 days prior to the first dosing, or concomitant participation in an investigational study involving no drug, vaccine, or device administration, or intent to participate in another clinical study at any time during the conduct of the study.
11. Use of medications for the timeframes specified below, with the exception of hormonal contraceptives and medications exempted by the Investigator on a case-by-case basis because they are judged to interfere with subject safety e.g., topical drug products without significant systemic absorption are permissible:
 - a. Prescription medication within 14 days prior to the first dosing that in the opinion of the Investigator could impact the subjects safe participation in the study;
 - b. Any medication, or treatments, that may affect the immune system such as allergy injections, immunoglobulin, interferon, immunomodulators, cytotoxic drugs, or other drugs known to be frequently associated with significant major organ toxicity within 90 days prior to enrolment;
 - c. Any registered vaccine administered within 30 days prior to enrolment in the study, or who plan to receive any non-study vaccines within 28 days of the second dose of the study vaccine
 - d. Any other investigational coronavirus vaccine i.e. SARS-CoV-1, SARS-CoV-2, MERS etc. at any time prior to, or during, the study.
 - e. Over-the-counter products within 7 days prior to the first dosing, that in the opinion of the investigator could impact the subjects safe participation in the study. Paracetamol (up to 2 g daily) and standard dose vitamins will be permitted.

12. Donation of plasma within 7 days prior to dosing. Donation or loss of blood (excluding volume drawn at screening) of 50 mL to 499 mL of blood within 30 days, or more than 499 mL within 56 days prior to the first dosing.
13. Receipt of blood products within 2 months prior to the first study treatment administration (Day 1), or planned receipt of blood products during the study period.
14. Breast-feeding subject, or subject who plans to breastfeed from the time of first dose through 60 days after last study treatment administration.
15. Presence of tattoos, scarring, skin discoloration, or any other skin disturbances at the injection site which, in the opinion of the Investigator, may inhibit the ability to effectively perform an injection site assessment.
16. Employee or immediate relative of an employee of the clinical site, any of its affiliates or partners, or Syneos Health.
17. Any reason which, in the opinion of the Investigator, would interfere with the primary study objectives or prevent the subject from participating in the study.
18. Permanent resident in an aged care facility (nursing or aged care home).

9. Clinical Procedures

Unless otherwise specified, procedures, data collection and evaluation will be conducted as per the clinical site SOPs.

9.1 Screening Procedures

Subject screening procedures will be performed within 28 days preceding administration of study medication. Subjects must provide written informed consent prior to initiation of any screening procedures. The consent to perform some general screening procedures may be obtained on a consent document other than the Informed Consent Form (ICF) specific to this study, and therefore, some screening test results could be obtained before signature of the ICF specific to this study. The study-specific ICF must be signed and dated by the subject before participation to study-specific procedures.

Screening procedures will include: demographic data, medical and medication histories, such as history of diabetes mellitus, hypertension and asthma, excluding childhood asthma, physical examination, body measurements, vital signs (BP, HR, RR, and TT), ECG, oxygen saturation (SpO₂), haematology, biochemistry, random blood sugar (non-fasting), coagulation (PT, APTT, and fibrinogen), serology (HIV, hepatitis B and C tests), SARS-CoV-2 test (nasal/oropharyngeal swab and RT-PCR, and serum antibodies by ELISA), urinalysis, serum pregnancy test, alcohol breath test, and urine drug screen.

Women not of childbearing potential must be post-menopausal, defined as cessation of regular menstrual periods for at least 12 months and confirmed by FSH level at screening, unless documented FSH and estradiol tests performed at the clinical site within 6 months prior to administration of the study medication are available. For women using hormone replacement

therapy and in whom FSH level have to be confirmed, this test will be performed at least one week following the withdrawal of the therapy, but before the first dosing.

For eligibility purposes, abnormal laboratory or vital signs results may be repeated at the discretion of the PI if an abnormal result is observed at the initial reading, however this discretion should be exercised on the side of caution. In the event that the participation of a subject in the study is delayed and some screening procedures had been performed outside of the prescribed screening window, outdated screening procedures may be repeated.

9.2 Clinical Visits and Follow-Up

Each subject will come for a visit to the clinical facility on Days 1 and 29 to be dosed with the study vaccine or placebo, according to their assigned randomised treatment.

Subjects will return on Days 2, 8, 29, 30, 36, and 57 for safety, including clinical laboratory safety, and immunological assessments.

Subjects will return on Days 15 and 43 for immunological assessments only.

Subjects will also return on Days 2 and 30, and 8 and 36 for a 24-hour and 7-day post-dose (respectively) safety assessment only.

In addition, subjects will be asked to return to the clinic at approximately 6 and 12 months post second dose (approximately Days 209 and 394) for a safety follow-up and blood draws for assessment of the duration of the immune response to the vaccine.

Subjects will be asked to return for an adhoc visit in early November where they will be informed of findings related to vaccine related HIV diagnostic interference. Subjects will receive written and verbal information on the potential for vaccination to elicit a reactive HIV results on some diagnostics and assured that this result does NOT indicate a HIV positive result.

A subset of subjects will also be asked to return at 3 months after their last dose (Day 120) for additional immunology assessment to evaluate the duration of HIV diagnostic cross-reactivity

9.3 Randomisation and Blinding

Subjects will be administered either a cohort specific SARS-CoV-2 Sclamp vaccine or placebo (Treatment A, B, C, or D, see Section 9.5), according to the randomisation scheme produced by Syneos Health. Eligible subjects will be allocated a randomisation number associated with a randomised treatment prior to dosing, as close to dosing as feasible (Day 1) in order to minimise the number of subject withdrawals in the period between randomisation allocation and dosing.

The subjects and the clinical personnel involved in the collection, monitoring, revision, or evaluation of AEs, or personnel who could have an impact on the outcome of the study will be blinded with respect to the subject's treatment assignment (SARS-CoV-2 Sclamp vaccine or placebo). Except for circumstances related to subject safety (see Section 7.1), blinding will be maintained at least until data collection of all subjects in each cohort up to Day 57 i.e., when reporting and evaluation of all AEs have been completed up to 28 days post-second dose.

After data is collected for all subjects up to Day 57 the collected data will be locked and the treatment assignment will be unblinded to all study team members for the purpose of data analysis and generation of the Clinical Study Report (CSR) Part 1 and Addendum to the CSR Part 2. Subjects will remain blinded for the remaining duration of the study, thus the study will adopt a single-blind design after Day 57.

Designated pharmacy personnel at the clinical site not directly involved with the clinical aspects of the trial will prepare and dispense the study medication and will be aware of the randomisation code and the treatment.

In the event of an emergency for an individual subject in which knowledge of the study treatment is critical to the subject's medical management, or for the decision of dose escalation, the Investigator, or another attending study physician, will break the blind for that subject. An envelope for each subject containing their treatment assignment will be available from the pharmacy personnel. The Investigator, or other attending study physician, will make every effort to contact the Sponsor prior to unblinding a subject's treatment assignment and will record the date and reason for unblinding in the study source documents. In the event the Sponsor cannot be contacted prior to unblinding, the Sponsor will be contacted at the earliest feasible time after the unblinding has occurred.

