7.1 Data Review by the Safety Review Committee

The SRC will be responsible for the assessment of available safety and tolerability data for each cohort and to make decisions with regards to study progression through the three cohorts in Part 1 and prior to initiating vaccination for Part 2. The SRC will be composed of at least the PI, one Sponsor representative, and a Syneos Health Medical Monitor. Additional non-voting members of the SRC may also be included in the SRC to contribute to discussions, but will not have a vote in the decision to progress to a new cohort. The conduct of the SRC during the study will be as dictated in the SRC Charter.

In Part 1, for the purpose of progressing from sentinels to dosing the rest of cohort (ROC), an informal SRC discussion will be held after the sentinel's safety data are available for 48-hours post dose (Day 2). If no AEs of note, SAEs, or severe AEs, dosing of the ROC may be conducted

without a formal SRC meeting, and dosing may commence with email confirmation from the SRC members (this process will be repeated again following administration of the second dose).

For the purpose of progressing from Cohort 1 to Cohort 2 and from Cohort 2 to Cohort 3, a formal SRC meeting will be held after aggregated safety and tolerability data up to at least Day 8 (7 days post-first dose) are available for all eligible subjects from each cohort before proceeding with vaccination of the next cohort (and similarly up to at least Day 36 following the second vaccination dose at Day 29). As the maximal immunological response is not expected to be reached by Day 8, immunological data will not be assessed as part of the SRC decision making process.

The potential decisions of the SRC are:

1. Escalate to the next planned dose level; or
2. Suspend dose escalation until further review of study data can be made, allowing the SRC to determine whether predefined halting rules have been met. Dose escalation may resume once the SRC concludes that no halting rules have been met; or
3. Stop dose escalation;
4. Terminate the study.

The SRC will conduct a blinded review of the data; however the blind may be broken for individual subjects if judged necessary, prior to making a decision on dose escalation. Dose escalation may occur only following mutual agreement between the SRC members. Decisions taken by the SRC will be documented and submitted to the HREC overseeing the study, along with supportive data.

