7.2 Dose Halting Rules

The following sections define halting rules, which are pre-defined criteria that halt the conduct of the study (either a single cohort or the entire study). These rules are to ensure the safety of study subjects. The following criteria including grading scales to be used in this study are based on the CBER (FDA) Guidance for Industry “Toxicity Grading Scale of Healthy Adult and Adolescent Volunteers Enrolled in Preventative Vaccine Clinical Trials”.⁴ Specific safety terms and reaction grading criteria are defined in Section 9.15.

Dosing of all subjects in a cohort shall be halted for any event suggesting that there is a significant safety risk to other subjects of the cohort, or when a clinically significant pattern of toxicity is apparent in more than one subject. The following events will result in a temporary halt of dosing within that cohort:

- The occurrence of a SAE assessed, as possibly or probably related to the study vaccine;
- The occurrence of a clinically significant unsolicited severe AE (Grade 3 AE), including vital signs, and/or a laboratory abnormality assessed as possibly or probably related to the study vaccine in ≥ 2 subjects in the same cohort; or
- 2 or more of the subjects enrolled in each cohort experience a severe (Grade 3):

- Allergic reaction (e.g., hives, angioedema, allergic asthma, systemic anaphylaxis) that is assessed as related to study vaccine; or
- Vaccine-related injection site ulceration, abscess, or necrosis.

If any of the above halting rules are met, dosing will be suspended for all subjects in that cohort, while continuation of other cohorts at lower or equivalent dose levels will be evaluated on a case-by-case basis. The SRC will review details of the event(s) and/or additional data. If, after further review of the data, the SRC determines that no halting rules have been met e.g., AE determined to be unrelated to the study vaccine, then dosing of the cohort may resume.

The Sponsor or the Investigator (after consultation with the Sponsor) has the right to discontinue the study at any time. If the clinical study is prematurely terminated, the clinical site must promptly inform the study subjects and must ensure that appropriate treatment and follow-up for the subjects is made available. The Sponsor must notify the HREC should the study be discontinued.

8. Study Population

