9.15.2 Recording of Adverse Events

Adverse events will be recorded and evaluated for their seriousness, severity, and relationship to the study medication. Adverse events will be collected and documented during the course of the study by appropriately trained and delegated medical staff in the clinic, as well as via self-reporting from subjects using the electronic diary. For a period of 12 months following the last study vaccine administration, adverse events will also be documented, if reported. Adverse events will be followed-up until complete resolution, or until the Investigator judges it to be safe to discontinue follow-up.

The term “reactogenicity” refers to solicited signs and symptoms (“solicited AEs”) occurring in the hours and days following vaccination, to be collected by the subject or legal representative(s) for 7 consecutive days, using an electronic Diary (eDiary) or paper Diary card (Diary).

The following solicited local and systemic AEs are included in the e-Diary. Solicited local reactions include erythema, swelling, and pain at the injection site. Solicited systemic reactions include fatigue, fever, headache, myalgia/arthralgia, chills, diarrhoea, nausea/vomiting.

Upon review of the subject diary, if a solicited local or systemic AE has been reported with a severity Grade=3 (severe), then the site is to confirm with the subject whether medical assistance was sought, was concomitant medication taken, and collect information around the event and outcome to document a safety assessment. In the event that the additional information leads to a determination that the solicited AE is deemed a Serious Adverse Event (SAE), the site will record the solicited AE as an SAE and report the event following the SAE reporting guidelines and time frames.

Each solicited AE is to be assessed using the toxicity grading provided in the scoring system adapted from the FDA Guidance for Industry -Toxicity Grading Scale for Healthy Adults and Adolescent Volunteers Enrolled in Preventive Vaccine Clinical Trials.⁴ Solicited AEs will be recorded as mild, moderate or severe by study subjects.

Table 2. Toxicity Grading for Solicited Local (Administration Site) Adverse Events

Local Reactions to Injection	Mild (Grade 1)	Moderate (Grade 2)	Severe (Grade 3)
Pain (at the vaccination site)	Does not interfere with activity	Repeated use of non-narcotic pain reliever >24 hours or interferes with activity	Any use of narcotic pain reliever or prevents daily activity

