9.15.4 Suspected Unexpected Serious Adverse Reactions

AEs that meet all of the following criteria will be classified as suspected unexpected serious adverse reactions (SUSARs) and reported to the appropriate regulatory authorities in accordance with applicable regulatory requirements for expedited reporting:

- Serious;
- Unexpected (i.e., the event is not consistent with the safety information in the IB); or
- There is at least a reasonable possibility that there is a causal relationship between the event and the study treatment

The investigator will assess whether an event is causally related to study treatment. The Sponsor (or Syneos Health) will consider the investigator's assessment and determine whether the event meets the criteria for being reportable as a 7-day or 15-day safety report. SUSARs that are fatal or life-threatening must be reported to the regulatory authorities and the HREC (where required) within 7 days after the Sponsor (or Syneos Health) has first knowledge of them, with a follow-up report submitted within a further 8 calendar days. Other SUSARs must be reported to the relevant regulatory authorities and the HREC within 15 calendar days after the Sponsor (or Syneos Health) first has knowledge of them.

The Sponsor (or Syneos Health) is responsible for reporting SUSARs and any other events required to be reported in an expedited manner to the regulatory authorities and for informing investigators of reportable events, in compliance with applicable regulatory requirements within specific timeframes. Investigators will notify the relevant HREC of reportable events within the applicable timeframes.

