11.1 Safety Measurements

Safety will be assessed by measuring the frequency and intensity of local and systemic solicited adverse events (AEs), unsolicited AEs, serious adverse events (SAEs), and safety laboratory data for all subjects. All solicited adverse events will be summarised according to the protocol defined severity grading scales. The proportion of subjects experiencing each adverse event will be presented for each symptom severity. Summary tables showing the occurrence of any local or systemic adverse event overall and at each time point will be presented.

Reactogenicity will be assessed by the proportion of subjects with solicited local and solicited systemic AEs up to 7 days after each vaccination and calculated for 3 time intervals after each vaccination: Days 1--3, Days 4--7, and Days 1--7. Post-administration solicited adverse events reported from Days 1-7 will be summarised by time interval, maximal severity and by vaccine group. The severity of solicited local adverse events, including injection site redness, swelling and induration will be summarised according to categories based on linear measurement: 2.5 to 5.0 cm, 5.1 to 10.0 cm and >10 cm.

Injection site pain and systemic reactions (except fever) occurring up to 7 days after each vaccination dose will be summarised according to “mild”, “moderate” or “severe”. Body temperature will be summarised by 0.5 °C increments from 36.0 °C up to ≥ 40 °C and will be reported by route of measurement.

Unsolicited AEs will be assessed by the proportion of subjects with any unsolicited AEs for 28 days after each vaccination.

The proportion of subjects with SAEs, TEAS, non-scheduled GP visits, unsolicited medically attended AEs, unsolicited AEs leading to study withdrawal or decision by the PI to discontinue with the second dose, will be collected from study start until study completion.

All spontaneously reported adverse events occurring during the study assessed by the Investigator as probably related, possibly related, or not related to vaccination will be recorded.

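### A code break for a dose-escalation decision can unblind the physician who rates causality, and the protocol neither fixes the blinded rating first nor says which rating is analysed

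*Protocol*

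**What the plan says.** **Breaking the code.** Protocol section 9.3 lets one subject's code be opened when an emergency makes the treatment critical to medical management "or for the decision of dose escalation, the Investigator, or another attending study physician, will break the blind for that subject". Pharmacy holds the envelopes. The steps required are an effort to reach the Sponsor and a record of the date and reason. The same section says that clinical staff who collect or evaluate AEs are blinded, with an exception for subject safety that points to section 7.1.

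**The escalation review.** Under section 7.1 the Safety Review Committee (SRC) reviews blinded data, but "the blind may be broken for individual subjects if judged necessary, prior to making a decision on dose escalation". On membership: "The SRC will be composed of at least the PI, one Sponsor representative, and a Syneos Health Medical Monitor". Escalation needs the agreement of the members, and SRC conduct is governed by a charter.

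**Who rates AEs.** Section 9.15.2: "Adverse events will be recorded and evaluated for their seriousness, severity, and relationship to the study medication". Section 9.15.4: "The investigator will assess whether an event is causally related to study treatment". Section 11.1 reports spontaneously reported events as "assessed by the Investigator as probably related, possibly related, or not related to vaccination will be recorded". Section 5.4 places intensity and relatedness of unsolicited AEs to Day 57 among the primary safety endpoints. Section 11.1 plans a separate summary of possibly or probably related events.

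**Halting rules.** Section 7.2 halts dosing in a cohort on SAEs, and on certain Grade 3 events, assessed as related. As an example of a review that ends a halt it gives "AE determined to be unrelated to the study vaccine, then dosing of the cohort may resume".

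**The concern.** The two reasons for a code break differ. In an emergency the treating physician needs to know the treatment. An escalation decision belongs to a committee and does not of itself require an AE rater to know it. Section 9.3 nevertheless gives both to the same clinical staff, and the Principal Investigator also sits on the SRC.

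Table 5 of the protocol defines relatedness in terms of the test vaccine. A rater who learns that the subject received saline will find a rating of possibly or probably related hard to sustain. A rater who learns that the subject received vaccine may be pulled the other way. The rating then partly reflects the allocation, and for those events the comparison with placebo loses meaning. The events concerned are likely to be the ones that matter most to the safety profile, and section 11.3 bases the choice of dose and regimen on that profile together with immunogenicity.

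**Working it through.** The protocol gives no figure to reproduce. The check is a reading of the sections against each other, followed by a simple scale.

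**1. Can an AE rater be unblinded for an escalation decision?** Yes. Section 9.3 names the Investigator or another attending study physician as the person who opens the code. Section 9.15.4 gives causality to the investigator.

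**2. Must a blinded rating exist first?** No. Section 9.3 requires only the contact effort and the record of date and reason. The halting rules in section 7.2 do presuppose a rating for the events they act on. But section 7.1 allows a break whenever it is judged necessary before an escalation decision and does not tie it to a halting event, so a prior rating is likely but not assured.

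**3. Is a later change kept out of the analysis?** No. Section 9.12 provides an audit trail in the data-capture system, so an edit would be visible. Section 11.1 tabulates the Investigator's assessment without saying whether the rating from before or after unblinding counts.

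**4. Which ratings are exposed?** Solicited AEs are graded by the subjects (section 9.15.2), who remain blinded (section 9.3). The exposure is therefore relatedness and intensity of unsolicited AEs.

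**5. How many subjects does one code reveal?** Normally one. Section 6 states that the Cohort 3 sentinels are 1 placebo and 1 active, so opening one of those codes reveals the other.

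**6. Scale.** Group sizes come from section 8.2. If the re-rated event is the subject's only related unsolicited AE, the shift in the proportion of subjects with a related AE is 1/n:

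| Group | n | Shift from one re-rated event |
|---|---|---|
| Vaccine group within a Part | 24 | 1/24 = 4.2 points |
| Placebo pooled within a Part | 3 × 8 = 24 | 1/24 = 4.2 points |
| Placebo kept by cohort | 8 | 1/8 = 12.5 points |

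If the subject has another related event, the any-related-AE rate does not move, and only the row for that event changes. The 1/n values give the size of one change, not its likelihood. The document offers no basis for estimating how often it would happen.

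**The case against.** The case against is substantial, and much of it stands.

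- *The rating usually comes first.* The halting rules act on events already assessed as related, and section 9.15.3 has SAEs reported within 24 hours. This stands as a description of the usual order. It does not make the order a requirement or stop a revision.
- *Edits are traceable.* True under section 9.12. Traceability shows that a rating changed; it does not decide which rating goes into the tables.
- *Code breaks are rare.* True. Review is blinded by default and breaks are individual. The point concerns few subjects.
- *Safety analysis is descriptive.* True. No test or error rate is affected, but a descriptive comparison that feeds dose selection can still be biased.
- *The SRC Charter may contain a safeguard.* Possible; it is not at hand. Sections 7.1 and 9.3 do not contain one.

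A reader might also infer from section 7.2 that the SRC overwrites the recorded relatedness. The text does not say so. It gives a finding of unrelatedness as an example of how a halt may end, without naming who makes it and without saying that the case report form is changed.

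A reader might conclude, too, that the code should be kept from the Investigator altogether, for instance by releasing it only to the medical monitor. The protocol does not support that as a plain correction. Escalation needs the agreement of the SRC members, and some would then have to agree without information judged necessary for the decision.

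**Conclusion.** The concern holds in a limited form. Section 9.3 allows a physician who rates AEs to be unblinded for an escalation decision, which works against its own statement that AE evaluators are blinded. The protocol neither fixes the blinded rating beforehand nor says which rating is analysed. For the few unsolicited AEs that prompt such a break, relatedness and intensity, both part of a primary safety endpoint, can be set or revised with the treatment known.

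The size is up to 4.2 percentage points per re-rated event in a group of 24. The 12.5-point figure applies only if placebo is tabulated by cohort. Section 11 speaks of comparison with the placebo group and does not settle the pooling, so both figures are shown. The shift assumes that the event is the subject's only related unsolicited AE.

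The document does not support the stronger reading that the Investigator alone or routinely opens codes, that severity grading in general is compromised, or that ratings will in fact be distorted. It shows an open route to bias, not an observed one. The point is worth making because closing that route costs very little.

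**What to change.** Add the following to sections 7.1 and 9.3:

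- Before any code break for an escalation decision, the Investigator's severity and causality for that subject's unsolicited AEs are entered and date-locked. Where one code reveals both sentinels, the same is done for the paired sentinel.
- The locked blinded entry is the one used in the safety tables.
- Any later re-determination, by the SRC or anyone else, is stored in a separate field.

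The emergency route and the SRC's decision authority stay as they are. Who on the SRC receives the code is left to the SRC Charter.

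The cost is a few sentences, one additional case report form field, and one extra data-entry step before an SRC code break. The lock cannot protect AEs that begin in the same subject after the break. The unblinding date already required by section 9.3 identifies those.
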